2.2 Trial Coordination / Monitoring

The Sponsor will coordinate the trial and will utilize the support of CROs for some activities of the trial. Sponsor will perform oversight of the activities performed by the CROs.

The Clinical Trial Supplies department of the Sponsor will supply the trial medication of avelumab. Packaging and distribution of clinical supplies will be performed by the Clinical Trial Supplies department of the Sponsor. First-line chemotherapy will be supplied by the study center or by the Sponsor, according to local laws and regulations.

Subject enrollment will be managed by an interactive web response system (IWRS). The Coordinating Investigator PPD represents all Investigators for decisions and discussions regarding this trial, consistent with the International Council for Harmonisation (ICH) Topic E6 Good Clinical Practice (GCP, hereafter referred to as ICH GCP). The Coordinating Investigator will provide expert medical input and advice relating to trial design and execution and is responsible for the review and sign-off of the clinical trial protocol.

Safety laboratory assessments will be performed centrally. Local laboratories may be used at the discretion of the Investigator as clinically needed for safety management of the subject, and results from the local laboratories will be entered in the electronic case report forms (eCRFs) per the eCRF Completion Guidelines; however, central laboratory results must also be collected. Urinalysis and urine pregnancy testing will be done locally only.

CCI and CCI assessments will be performed under the responsibility and / or supervision of the Sponsor.

The Global Drug Safety Department, Merck KGaA, Darmstadt, Germany, or their designated representatives will supervise drug safety and the timely reporting of adverse events (AEs) and serious adverse events (SAEs).

Quality assurance of the trial conduct will be performed by the Research & Development Quality Department, Merck KGaA, Darmstadt, Germany.

The department of Global Biostatistics will supervise the statistical analyses (with the exception of the **CCI** data analyses), which will be outsourced to a CRO. The trial will appear in the following clinical trial registry: ClinicalTrials.gov

2.3 Review Committees

2.3.1 Independent Data Monitoring Committee

An Independent Data Monitoring Committee (IDMC) will be composed of a minimum of 3 members who do not have any conflict of interests with the trial Sponsor, including 2 clinicians and a biostatistician. The IDMC will periodically review safety data. The full membership, mandate, and processes of the IDMC will be detailed in the IDMC charter.

2.3.2 Independent Radiologist

An independent radiologist verifies and confirms eligibility to enter the Maintenance Phase.

3 Background Information

3.1 Gastric Cancer

Globally, gastric cancer is the fifth most common cancer and the third leading cause of cancer death. In 2012, there were approximately 950,000 new cases and 723,000 deaths worldwide (Stewart 2014). Of these cancers, approximately 90% to 95% were adenocarcinomas with the remaining 5% to 10% comprising of neuroendocrine tumors, lymphomas, squamous cell cancer, and sarcomas.

The incidence of gastric cancer varies widely by country, with no true global standard treatment established. Higher incidence rates are observed in Asia, Costa Rica, Peru, and Eastern Europe, while Western Europe and the USA have lower incidence rates (Globocan 2012).

Chemotherapy is routinely used to treat metastatic gastric cancer; however, there is no single standard regimen that is used globally. Common chemotherapy agents used to treat gastric cancer, either as monotherapy or in combination, include the following: fluorouracil (5-FU) and other fluoropyrimidines (eg, capecitabine, S1), carmustine, semustine and doxorubicin, mitomycin C, cisplatin, oxaliplatin, taxanes, and irinotecan. The relative benefits of these different drugs, alone and in combination, are unclear (NCCN 2015). Recently, trastuzumab has become available for use with chemotherapy for the treatment of patients whose tumors overexpress the human epidermal growth factor receptor 2 gene (Hudis 2007). Despite the availability of these agents, advanced, unresectable, and/or metastatic gastric cancer remains a significant unmet medical need.

3.2 Programmed Death Receptor and Ligands

The programmed death 1 (PD-1) receptor and PD-1 ligands 1 and 2 (PD-L1, PD-L2) play integral roles in immune regulation. Expressed on activated T-cells, PD-1 is activated by PD-L1 and PD-L2 expressed by stromal cells, tumor cells, or both, initiating T-cell death and localized immune suppression (Dong 1999; Dong 2002; Freeman 2000; Topalian 2012a), potentially providing an immune-tolerant environment for tumor development and growth. CCI

In the clinical setting, treatment with antibodies that block the PD-1 – anti-PD-L1 interaction have been reported to produce objective response rates (ORR) of 7% to 38% in patients with advanced or metastatic solid tumors, with tolerable safety profiles (Hamid 2013; Brahmer 2012; Topalian 2012b). Notably, responses appeared prolonged, with durations of 1 year or more for the majority of patients. Recent studies have documented the activity of anti-PD-L1 antibodies in subjects with advanced gastric cancer (Muro 2014; Lutzky 2014).

3.3 Avelumab

The investigational medicinal product (IMP) for the present trial is avelumab. Avelumab is a fully human monoclonal antibody of the immunoglobulin (Ig) G1 isotype. Avelumab selectively binds to PD-L1 and competitively blocks its interaction with PD-1. Compared with anti-PD-1 antibodies that target T-cells, avelumab targets tumor cells and is therefore expected to have fewer side effects, including a lower risk of autoimmune-related safety issues, as blockade of PD-L1 leaves the PD-L2/PD-1 pathway intact to promote peripheral self-tolerance (Latchman 2001). For complete details of the in vitro and nonclinical trials, please refer to the Investigator’s Brochure (IB).

In light of the recent data demonstrating the clinical efficacy of an anti-PD-L1 antibody in advanced gastric cancer, and given the clinical importance of PD-L1 expression in gastric cancer tumor cells (Oki 2014) and the mode of action of avelumab, avelumab is being developed as a potential therapy for patients with various advanced solid tumors, including gastric cancer. This anti-PD-L1 therapeutic antibody concept is intended to be developed in oncological settings by Merck KGaA, Darmstadt, Germany, and by its subsidiary, EMD Serono R&D.

The ongoing trials for avelumab are described in the IB. Avelumab is currently in clinical development with 2 ongoing Phase I trials in subjects with solid tumors, one ongoing Phase II trial in Merkel cell carcinoma (MCC), and 2 Phase III trials in non-small cell lung cancer (NSCLC). Of the ongoing studies, 2 of these studies have cohorts of patients with advanced gastric cancer:

- Trial EMR100070-001 is “a Phase I, open-label, multiple-ascending dose trial to investigate the safety, tolerability, PK, biological, and clinical activity of avelumab in subjects with metastatic or locally advanced solid tumors.”
- Trial EMR100070-002 is “a Phase I trial to investigate the tolerability, safety, PK, biological, and clinical activity of avelumab in Japanese subjects with metastatic or locally advanced solid tumors, with expansion part in Asian subjects with gastric cancer.”

In addition to the trial described in this protocol, EMR100070-007, another Phase III study in patients with advanced gastric cancer (EMR100070-008) is ongoing for third-line treatment.

3.3.1 Safety

Available safety and efficacy data for the avelumab program are discussed in the IB and establish a positive benefit risk for conducting Phase III studies with 10 mg/kg (the dosing used in this trial).

[figure not shown]
The safety profile of avelumab has been evaluated from data of more than 1,750 subjects, including all subjects treated with 10 mg/kg from studies EMR100070-001 (1,650 subjects) and EMR100070-003 Part A (88 subjects as pooled safety dataset with a data cut-off of 09 June 2016) and subjects in the ongoing local Japanese Phase I EMR100070-002. These safety data from subjects with different tumor types treated with avelumab suggests an acceptable safety profile of the compound. Most of the observed events were either in line with those expected in subjects with advanced solid tumors or with similar class effects of monoclonal antibodies blocking the PD-1/PD-L1 axis. Infusion-related reactions including drug hypersensitivity reactions, and immune-mediated adverse reactions (immune-related pneumonitis, immune-related colitis, immune-related hepatitis, immune-related endocrinopathies [thyroid disorders, adrenal insufficiency, new onset Type I diabetes mellitus, pituitary disorders], immune-related nephritis, and renal dysfunction and other immune-related AEs [myositis, myocarditis, Guillain-Barre syndrome, uveitis]) have been identified as important risks for avelumab (please see current IB for details). Detailed guidelines for the management of immune-related AEs and infusion-related reactions have been implemented in the study protocols, including this one (please see Section 3.5, Section 5.1.2.2.1, Section 5.1.3.2, Section 6.2.1, Section 6.4, Section 6.5.4, Section 6.5.5, and Section 6.12).

3.3.2 Pharmacokinetic Results

Draft PK assessments have been performed in ongoing Trials EMR100070-001 and EMR100070-002. The preliminary results based on the data available as of 19 December 2014 are presented under the individual trial headings.

3.4 Rationale for the Current Clinical Trial

The safety and clinical efficacy of avelumab have been determined in multiple tumor types (NSCLC, ovarian cancer, mesothelioma, melanoma, thymoma, and adrenocortiocarcinoma) (Disis 2015, Gulley 2015). The rationale to enroll subjects with unresectable locally advanced or metastatic adenocarcinoma of the stomach or gastroesophageal junction (GEJ) is supported by data reported from other PD-1/PD-L1 agents and from 2 expansion cohorts in 2 avelumab Phase I studies.

3.4.1 Data from Anti-PD-1/PD-L1 Therapies in Gastric Cancer

Data from other anti-PD-1/PD-L1 therapies in gastric cancer are as follows:

- Data presented at the American Society for Clinical Oncology Annual Meeting 2014 from a Phase I expansion cohort of 16 subjects with gastroesophageal cancer treated with MEDI4736 (anti-PD-L1), which reported 4 out of 16 responders ([Lutzky 2014](#)).
- Data presented at the European Society for Medical Oncology Annual Meeting 2014 from a Phase I cohort of 39 PD-L1+ subjects with advanced gastric cancer treated with anti-PD-1 (Keynote012), which reported 12 out of 39 responders ([Muro 2014](#)).

3.5 Summary of the Overall Benefit and Risk

Based on the nonclinical and Phase I data available to date, the conduct of the trial is considered justifiable using the dose and dose regimen of the avelumab as specified in this clinical trial protocol. An IDMC (see Section 2.3.1) will assess the risk-benefit ratio on an ongoing basis. The trial will be discontinued in the event of any new findings that indicate a relevant deterioration of the risk-benefit relationship that would render continuation of the trial unjustifiable.

The primary known identified risks of exposure to avelumab include:

- Infusion-related reactions
- Immune-related adverse events (irAEs).

To mitigate the risk of infusion-related reactions, premedicate patients with an antihistamine and with paracetamol (acetaminophen) prior to the first 4 infusions of avelumab. Premedication should be administered for subsequent avelumab doses based upon clinical judgment and presence/severity of prior infusion reactions. This regimen may be modified based on local treatment standards and guidelines as appropriate provided it does not include systemic corticosteroids.

In addition, since avelumab can induce antibody-dependent cell-mediated cytotoxicity (ADCC), there is a potential risk of tumor lysis syndrome (see Section 6.5.4.3).

As noted in Section 3.2, trials with antibodies that block the PD-1 – PD-L1 interaction have been reported to produce ORR of 7% to 38% in patients with advanced or metastatic solid tumors, with response durations of 1 year or more for the majority of patients.

This clinical trial will be conducted in compliance with the clinical trial protocol, ICH GCP, and the applicable national regulatory requirements.

4 Trial Objectives

4.1 Primary Objectives

- The primary objectives of this trial are to demonstrate superiority of maintenance therapy with avelumab versus continuation of first-line chemotherapy with regard to Overall Survival (OS) in all randomized subjects or in PD-L1+ subjects who have not progressed on first-line chemotherapy.

4.2 Secondary Objectives

Secondary objectives are as follows:

- To demonstrate superiority of maintenance therapy with avelumab versus continuation of first-line chemotherapy with regard to PFS as per RECIST v1.1 according to Investigator assessment.
- To demonstrate superiority of maintenance therapy with avelumab versus continuation of first-line chemotherapy with regard to the ORR as per RECIST v1.1 and per Investigator assessment
- To compare the subject-reported outcomes / quality of life (QoL) of subjects when treated with avelumab versus continuation of first-line chemotherapy as assessed by the European QoL 5-dimensions 5 Level Questionnaire (EQ-5D-5L), and the European Organization for Research and Treatment of Cancer (EORTC) QLQ-C30 and module QLQ-STO22
- To determine the safety and tolerability of avelumab.

5 Investigational Plan

5.1 Overall Trial Design and Plan

This is a multicenter, international, randomized, open-label Phase III trial comparing maintenance therapy with avelumab with continuation of first-line chemotherapy in subjects with unresectable, locally advanced or metastatic, adenocarcinoma of the stomach, or of the GEJ (See Sections 5.1.2.1 and 5.1.2.2 for details).

The medicinal products oxaliplatin, 5-FU and capecitabine are used as chemotherapy agents in the Induction Phase and the Maintenance Phase of this trial. All three substances are accepted as standard of treatment for the indication under study. Before administering any of these substances, the Investigator is required to refer to what is stated in the current product information (local label, Summary of Product Characteristics [SmPC]), particularly in regard to contraindications, warnings and precautions for use, dosage adjustments in the event of toxicity, patient monitoring provisions, the duration of the need for contraception, and medicinal products that are prohibited or that must be used with caution. In case of a potential contradiction between the specifications outlined in this clinical trial protocol and the information contained in the product information (local label, SmPC) of oxaliplatin, 5-FU, or capecitabine, the local label always prevails. Investigators should check updated labeling via relevant websites before enrollment, randomization, and chemotherapy administration in the Induction Phase and the Maintenance Phase.

This study is conducted with a Screening period and an Induction Phase, Maintenance Phase, and Follow-up Phase.

5.1.1 Overall Design

Approximately 466 subjects are planned to be enrolled in the Maintenance Phase. The actual number of subjects enrolled in the Induction Phase will be driven by observed induction failure rates and will be such to allow for approximately 466 patients to be randomized in the Maintenance Phase. At the time of this protocol amendment, subject enrollment in the Maintenance Phase is complete, with 499 subjects randomized into the Maintenance Phase. Subjects enrolled in the Induction Phase will receive a first-line therapy comprised of oxaliplatin and either 5-FU or capecitabine (Induction Phase) for 12 weeks (see Section 5.1.2.1).

Following the Induction Phase, subjects who experience a CR, PR, or SD after 12 weeks (approximately 466 subjects) will be randomly assigned (Maintenance Phase) to receive either avelumab (see Section 5.1.2.2.1) or continuation of the same regimen of chemotherapy from the Induction Phase (see Section 5.1.2.2.2). Subjects who are not deemed eligible to receive further chemotherapy will receive best supportive care (BSC) alone with no active therapy.

Prior to randomization, Investigators must specify which of treatments (continuation of the same regimen of chemotherapy from the Induction Phase versus BSC) will be selected for subjects in chemotherapy control arm.

CCI

After the Induction Phase, all subjects will be evaluated for eligibility into the Maintenance Phase by an independent radiologist using RECIST v1.1.

Study treatment will continue until:

- Disease progression (see Section 5.5.1)
- Significant clinical deterioration (clinical progression) by Investigator's opinion
- Unacceptable toxicity per Investigator opinion, or
- Any criterion for withdrawal from the trial or trial treatment is fulfilled (see Section 5.5).

Subjects receiving avelumab may continue treatment past the initial determination of disease progression per RECIST v1.1 as long the following criteria are met:

- Investigator-assessed clinical benefit, without any rapid disease progression
- Tolerance of trial treatment
- Stable Eastern Cooperative Oncology Group (ECOG) performance status (PS) (PS = 0 or 1)
- Treatment beyond progression will not delay an imminent intervention to prevent serious complications of disease progression (for example, central nervous system metastases).

The decision to continue avelumab treatment beyond progression should be discussed with the Medical Monitor and documented in the study records.

For subjects continuing avelumab after initial progressive disease (PD), a radiographic assessment should be performed within 6 weeks of original PD to determine whether there has been a decrease in the tumor size, or continued PD. The assessment of clinical benefit should be balanced by clinical judgment as to whether the subject is clinically deteriorating and unlikely to receive any benefit from continued treatment with avelumab.

For subjects receiving avelumab, if discontinuation occurs due to progression and a definitive diagnosis/radiographic confirmation is not made at the time of discontinuation, a second imaging

scan may be allowed for confirmation of progression. If progression at the second imaging scan is not confirmed and the subject wishes to restart, the subject will be allowed to continue receiving avelumab as long as they meet the criteria for continuation of treatment beyond progression.

If the Investigator feels that the subject continues to achieve clinical benefit by continuing treatment, the subject should remain on the trial and continue to receive monitoring according to the Schedule of Assessments (Table 3).

Any additional continuation of avelumab plus BSC beyond further progression must be discussed and agreed upon with the Medical Monitor. Further disease progression is defined as an additional increase in tumor burden of 20% and ≥ 5 mm absolute increase in tumor burden from time of initial PD. This includes an increase in the sum of all target lesions and/or the development of new measurable lesions.

Subjects receiving avelumab who have experienced a CR should be treated for a minimum of 12 months or until disease progression or unacceptable toxicity, after confirmation of response. In case a subject with a confirmed CR relapses after stopping treatment, but prior to the end of the trial, 1 re-initiation of treatment is allowed at the discretion of the Investigator and after agreement with the Medical Monitor. To be eligible for retreatment, the subject must not have experienced any toxicity that led to treatment discontinuation of the initial avelumab therapy. Subjects who re-initiate treatment will stay on trial and will be treated and monitored according to the protocol and follow the Schedule of Assessments until disease progression (see Table 3).

Subjects receiving maintenance chemotherapy will receive trial treatment until PD per RECIST version 1.1, for the accepted maximal duration of the agent(s) selected, significant clinical deterioration (clinical progression), unacceptable toxicity, withdrawal of consent, or if any criterion for withdrawal from the trial or trial treatment is fulfilled.

On-study subject management and study endpoint evaluation will be based on Investigator assessments (see Section 7.3).

[figure not shown]
Subjects will attend clinic visits at regular intervals to receive trial treatment and for efficacy and safety assessments (see Section 7.1).

The primary endpoint of the trial is OS, defined as the time (in months) from randomization to the date of death, regardless of the actual cause of the subject's death. The primary endpoint OS will be tested in all randomized subjects (intent-to-treat [ITT] Analysis Set) and in PD-L1+ subjects (PD-L1+ Analysis Set). The PD-L1 expression status will be determined according to the conventional tumor-cell (cell number-based percentage) scoring method where subjects with PD-L1 tumor expression $\geq 1\%$ are considered to be PD-L1+.

Safety endpoints include AEs, assessed throughout the trial and evaluated using the NCI-CTCAE v4.03; physical examinations; clinical laboratory assessments; concomitant medications; vital signs; electrocardiogram (ECG) parameters; and ECOG PS.

The trial design schematic is presented in Figure 1.

Figure 1 Schematic of Trial Design

All subjects in both arms will receive BSC as background therapy as specified in Section 6.1.4. BSC=best supportive care; 5-FU=5-fluorouracil; n=number of subjects; PD=progressive disease.

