8.1 Sample Size

The sample size of this study is based on comparing maintenance therapy avelumab versus continuation of first-line chemotherapy in terms of the two primary hypotheses (for hierarchy of multiple testing procedure, see Section 8.5.1) of OS in all randomized subjects and in PD-L1+ subjects.

The study will be considered successful if at least one of the two null hypotheses for OS in either all randomized subjects or in PD-L1+ subjects, could be rejected as statistically significant. An imbalanced type I error allocation will be used for the two primary hypotheses and control overall family wise type I error rate at 2.5% (1-sided) with 0.5% (1-sided) allocated to PD-L1+ subjects and 2% (1-sided) allocated to all randomized subjects. The sample size for this study is driven by the following assumptions for the primary endpoint of OS:

- Exponential distribution of OS;
- 1:1 randomization;
- Drop-out rate = 5%;
- Uniform accrual over a period of 18 months;
- A follow-up time of 18 months after randomization of the last subject;

- For all randomized subjects receiving avelumab, median OS is 15 months;
- For PD-L1+ subjects receiving avelumab, the median OS is 19.3 months;
- For all randomized subjects and PD-L1+ subjects receiving first-line chemotherapy, the median OS is 10.5 months.

This corresponds to a hazard ratio (HR) of 0.7 for OS in all randomized subjects and 0.54 for OS in PD-L1+ subjects. At planning stage, it was assumed that the prevalence of PD-L1+ subjects in all randomized subjects is 35%. Due to a lower prevalence of PD-L1+ subjects in the study than initially expected, the targeted 112 OS events in PD-L1+ subjects for the primary analysis will not be reached during the study. The primary analysis of OS in PD-L1+ subjects will be conducted at the time of the primary analysis of OS in all randomized subjects with power less than 80%.

The assumed drop-out rate for OS is based on respective experience in previous clinical studies.

The actual number of subjects enrolled in the Induction Phase will be driven by the observed induction failure rates, and will be such to allow for approximately 466 subjects to be randomized into the treatment arm in the Maintenance Phase. At the time of this protocol amendment, subject enrollment into the Maintenance Phase is complete, with a total of 499 subjects randomized into the Maintenance Phase.

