8.5.2 Analysis of Primary Endpoint

Primary Analysis

The primary endpoint for maintenance therapy is OS. The two primary analysis sets will be the ITT Analysis Set and the PD-L1+ Analysis Set. The following analysis will be conducted in the same manner for both ITT and PD-L1+ Analysis sets. The difference between the two treatment arms will be compared using a stratified, 1-sided, log-rank test. The stratification factor will be region (Asia versus non-Asia). Control of type I error and statistical significance is discussed in Section 8.5.1. The following null hypothesis will be tested:

$$H_0: \lambda_A(t) / \lambda_B(t) \geq 1, \text{ versus } H_1: \lambda_A(t) / \lambda_B(t) < 1$$

where $\lambda(t)$ represents the hazard rate (corresponding to each endpoint) at time t for treatment arms A (avelumab) and B (continuation of the same chemotherapy regimen/BSC).

A stratified Cox proportional hazards model will be used to assess treatment effect between the two treatment arms and to explore the robustness of the primary endpoint confirmatory analysis. The natural parameter of this model is the log hazard ratio. Each stratum will define a separate baseline hazard function. Ties will be handled by replacing the proportional hazards model by the discrete logistic model. The hazard ratio of avelumab versus maintenance chemotherapy/BSC (with maintenance chemotherapy/BSC as reference) together with the corresponding Wald 2-sided 95% CIs will be presented.

Kaplan-Meier (ie, product-limit) estimates of median OS will be presented by treatment arm together with 2-sided 95% CIs calculated according to [Brookmeyer and Crowley \(1982\)](#). Finally, the number of subjects at risk vs. failed along with Kaplan-Meier estimates of survival probability (often referred to as “survival rate”) at 3, 6, 9 and 12 months will be estimated with corresponding 2-sided 95% CIs derived using the log-log transformation according to [Kalbfleisch and Prentice \(1980\)](#).

The number and percentage of subjects with observed OS events will be presented by treatment arm (avelumab or maintenance chemotherapy/BSC). In addition, frequency counts for censoring reason will be presented by treatment group.

Sensitivity Analyses

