secondary efficacy endpoint (reported outcomes / QoL assessed by the EQ-5D-5L, EORTC QLQ-C30, and EORTC module QLQ-STO22 questionnaires) analyses will be conducted in this interim analysis. See Sections 8.5.1 and 8.5.3 for details regarding the hierarchical testing strategy to be used. If at the time of this interim analysis, the analysis is performed with exactly 267 deaths observed (75% planned information fraction), the OS in all randomized subjects of avelumab-assigned subjects is shown to be superior to that of subjects randomly assigned to the maintenance chemotherapy/BSC arm with a p-value of < 0.0072 the IDMC may declare superior efficacy in the avelumab treatment arm compared with the maintenance chemotherapy/BSC arm and recommend that the trial be stopped early. The IDMC will also be presented with subject disposition, demographic information, baseline disease characteristics, and safety information. An independent statistical provider will perform the interim analyses to support the IDMC. Details will be documented in a separate SAP or IDMC charter. Results from the interim analyses will be transmitted from this group to the IDMC only. Trial staff involved with the day to day management of the trial as well as any Sponsor staff will not have access to this interim information. Details of the IDMC mission, composition, and operations will be provided in the IDMC charter.

9 Ethical and Regulatory Aspects

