## 5 Summary of Clinical Trial Features

Trial objectives	
Primary objectives: The primary objectives are to demonstrate superiority of maintenance therapy with avelumab versus continuation of first-line chemotherapy with regard to Overall Survival (OS) in all randomized subjects or in PD-L1+ subjects who have not progressed on first-line chemotherapy.
 
Secondary objectives:
 

• To demonstrate superiority of maintenance therapy with avelumab versus continuation of first-line chemotherapy with regard to Progression-Free Survival (PFS) as per Response Evaluation Criteria in Solid Tumors version 1.1 (RECIST v1.1) and per Investigator assessment.

• To demonstrate superiority of maintenance therapy with avelumab versus continuation of first-line chemotherapy with regard to objective response rate (ORR) as per RECIST v1.1 according to investigator assessment.

• To compare the subject-reported outcomes / quality of life (HRQoL) of subjects when treated with avelumab versus continuation of first-line chemotherapy as assessed by the European QoL 5-dimensions 5-levels questionnaire (EQ-5D-5L), and the European Organization for Research and Treatment of Cancer (EORTC) QLQ-C30 and module QLQ-STO22

• To determine the safety and tolerability of avelumab

-------------------------	---

CCI

	

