## 10 General Specifications for Statistical Analyses

For the Induction Phase, all the analyses performed will be presented by the two chemotherapy arms and overall, unless otherwise specified. For the Maintenance Phase, demographic and baseline characteristics, as well as all the safety and efficacy endpoint analyses will be summarized by avelumab arm and the combined chemotherapy/BSC arm.

All statistical analyses will be performed using SAS® Version 9.4 or higher.

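### The objectives name continued first-line chemotherapy as the comparator, the primary OS test uses a pooled chemotherapy/BSC control, and no visible OS analysis uses the pre-randomization choice between the two

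*Protocol*

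**What the plan says.** **Objectives.** Protocol 4.1 sets out "to demonstrate superiority of maintenance therapy with avelumab versus continuation of first-line chemotherapy with regard to Overall Survival". Protocol 4.2 uses the same comparator: "To demonstrate superiority of maintenance therapy with avelumab versus continuation of first-line chemotherapy with regard to PFS". SAP Section 5 repeats it: "superiority of maintenance therapy with avelumab versus continuation of first-line chemotherapy with regard to Overall Survival (OS". None of these mentions BSC.

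**Planning assumption.** Protocol 8.1 states: "For all randomized subjects and PD-L1+ subjects receiving first-line chemotherapy, the median OS is 10.5 months". The synopsis attaches the same 10.5 months to the control arm as a whole. Neither place mentions a BSC component.

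**Test.** Protocol 8.5.2 defines the hazards compared as those of arms "A (avelumab) and B (continuation of the same chemotherapy regimen/BSC"; SAP 15.1 and 15.1.1 do likewise. The interim claim in Protocol 8.6 is that avelumab OS is "superior to that of subjects randomly assigned to the maintenance chemotherapy/BSC arm". SAP Section 10 says "all the safety and efficacy endpoint analyses will be summarized by avelumab arm and the combined chemotherapy/BSC arm". By contrast, SAP 15.2.2 defines the ORR odds ratio against chemotherapy alone.

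**Designation.** Protocol 5.1.1 requires the investigator to specify, before randomization, which option applies: "continuation of the same regimen of chemotherapy from the Induction Phase versus BSC) will be selected for subjects in chemotherapy control arm". SAP Section 10 (Study Treatment Phases) describes the control treatment as prespecified by the physician, and SAP Section 14 places the eligibility judgment at the end of induction.

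**The concern.** The objective asks whether avelumab beats continued chemotherapy. The test asks whether it beats a mixture of continued chemotherapy and BSC. If some control subjects receive no active therapy and fare worse for it, part of any observed benefit comes from them.

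The plan already requires the one piece of information that could separate the two sources: the investigator's choice, made before allocation. No visible OS analysis uses it. If it stays unused, a report of superiority over first-line chemotherapy would claim more than the visible analyses can support.

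**Working it through.** **1. Where the designation is used**

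| Place in the plan | Uses the chemotherapy/BSC designation for OS? |
|---|---|
| Primary log-rank and Cox (Protocol 8.5.2; SAP 15.1, 15.1.1) | No; stratified by region only |
| The 15 subgroups in SAP Section 9 | No; induction regimen is listed, the designation is not |
| Visible OS sensitivity analyses (SAP 15.1.2): unstratified, 356-event cut-off, censoring at subsequent therapy, RMST | No |
| Per-protocol set (SAP Section 9) | No; subjects who get no active treatment stay in |
| Disposition, safety and HRQoL sets, treatment-date rules (SAP 9, 10, 11.1) | BSC status is used, but not for OS |

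SAP 15.1.3 and parts of 15.1.2 and 15.1.4 are blacked out, so this covers visible text only.

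**2. Reproducing the plan's figures**

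Inputs from Protocol 8.1 and 8.6: HR 0.70, 1-sided 2%, looks at 267 and 356 events, Lan-DeMets O'Brien-Fleming spending.

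- Interim: 2[1 - Φ(2.326/√0.75)] = 0.0072, z = 2.446.
- Final: z = 2.101, p = 0.0178.
- Power at 356 events: 90.07%; 355.1 events are needed for 90%.

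All agree with the plan. The calculation has a single 10.5-month control and no BSC component.

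**3. Chance of an ITT win when avelumab equals chemotherapy**

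The BSC share b and the HR versus BSC are assumptions; the documents give neither. Approximate the pooled effect as log HR = b × ln(HR versus BSC), with HR 1.0 versus chemotherapy. Then P(win) = P(Z1 > 2.446 or Z2 > 2.101), with means -log HR × √267/2 and -log HR × √356/2 and correlation √(267/356).

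Example: b = 10% and HR 0.7 give log HR = 0.10 × ln 0.7 = -0.0357, pooled HR 0.965, means 0.291 and 0.336, and P(win) = 4.3%.

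| HR versus BSC | b = 5% | b = 10% | b = 20% |
|---|---|---|---|
| 1.0 | 2.0% | 2.0% | 2.0% |
| 0.85 | 2.4% | 2.9% | 4.0% |
| 0.7 | 3.0% | 4.3% | 8.2% |
| 0.5 | 4.2% | 8.0% | 22.4% |

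The approximation runs high in the bottom right corner. Simulation (499 subjects, exponential survival, chemotherapy median 10.5 months, 18-month accrual, drop-out taken as 5% per year) gives 20.0-20.6% there, and 16.2% if BSC-designated subjects have 1.5 times the hazard. A separate simulation with 466 subjects and BSC medians of 6 to 8 months gives 2.2-3.5%, 3.3-6.2% and 5.7-13.9% at shares of 5%, 10% and 20%.

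**4. Cost of restricting to chemotherapy-designated subjects in both arms**

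Events = 356 × (1 - b). 95% CI factor = exp(1.96 × 2/√events). Power at HR 0.70, 1-sided 0.025 = Φ(0.357 × √events/2 - 1.96).

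| b | Events | CI factor | Power | Events in the BSC stratum (CI factor) |
|---|---|---|---|---|
| 0 | 356 | 1.23 | 92% | none |
| 5% | 338 | 1.24 | 91% | 18 (2.5) |
| 10% | 320 | 1.24 | 89% | 36 (1.9) |
| 20% | 285 | 1.26 | 85% | 71 (1.6) |

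In the first simulation, the restricted analysis rejects in 2.2-2.8% of trials when HR versus chemotherapy is 1.0, close to its nominal 2.5%.

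**The case against.** **BSC is disclosed as part of the arm.** The synopsis and Protocol 5.1.2.2.2 and 5.2.6 all place BSC under the chemotherapy arm, and the hypothesis, hazard ratio and interim claim all say chemotherapy/BSC. A reader might infer that the pooling is hidden or improvised. It is neither, and the wording point on its own is small.

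**The test is sound.** A reader might infer that type I error is inflated. It is not. Wins of the kind in step 3 with an HR below 1 versus BSC are correct rejections of the pooled null.

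**The effect may be nil.** Protocol 5.2.3 says no data show that chemotherapy beyond 4 to 6 cycles improves survival, which leaves equivalence of chemotherapy and BSC open. Exclusion criterion 23 and the single-agent option may also keep the BSC share low. This stands. A reader might take a chance of around 20% as the likely size, but that needs both a 20% share and HR 0.5, neither of which the documents support.

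**The analysis may exist in redacted text.** This stands as a limit: the claim cannot go beyond what is visible.

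**The designation may not be available for both arms.** SAP Section 9 shows an IWRS record only for control subjects, and the disposition cross-tabulation in SAP 11.1 keeps avelumab as one category. But a choice made before allocation must have been made for every randomized subject. Its making is established; its storage for avelumab subjects is not shown, so the fix is conditional.

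**Conclusion.** The point holds and is minor. The objectives name continued first-line chemotherapy, the valid primary test uses pooled chemotherapy/BSC, and the visible plan cannot show how far a win reflects benefit over chemotherapy. The 356 events, the boundaries and the error control stand.

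A reader might also infer that the 10.5-month assumption refers throughout to chemotherapy alone. Protocol 8.1 does say that, but the synopsis says control arm, so this is an inconsistency and not a demonstrated planning error.

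The plausible size is modest. With HR 1.0 versus chemotherapy and an assumed HR of 0.7-0.85 versus BSC, an ITT win has a chance of about 2.4-3.0%, 2.9-4.3% and 4.0-8.2% at BSC shares of 5%, 10% and 20%. The share and both HRs are assumptions. Disposition tables will report the share, but not OS by designation.

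**What to change.** 1. In SAP 15.1.2, add one supportive OS analysis: repeat the region-stratified log-rank and Cox analysis in FAS subjects designated to chemotherapy before randomization, in both arms. Report BSC-designated subjects descriptively only. First confirm that the designation is stored for avelumab subjects; if it is not, omit this analysis and say why. Restricting both arms on a pre-allocation choice keeps the randomized comparison.
2. State the conclusion as superiority over chemotherapy/BSC, and align the odds-ratio wording in SAP 15.2.2.

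**Cost.** One SAP paragraph, one table and some wording. Protocol 8.5.2 already allows further sensitivity analyses in the SAP, so item 1 needs no protocol amendment. Rewording the protocol objective itself would need one (Protocol 10.5), so the conclusion wording can be set in the SAP and the report instead. The restricted analysis has a slightly wider interval (factor about 1.24-1.26 against 1.23). The primary test, alpha and stratification do not change.
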